Study Protocol Title

**A Randomized phase II clinical trial to evaluate the efficacy alternating
mFOLFOX/mFOLFIRI chemotherapy regimen
as a second-line treatment for advanced biliary tract cancer**

Version No: ver. 1.3_2025.01.17

Principal Investigator's Affiliation
: Department of Hematology and Oncology,
Seoul National University Bundang Hospital

Principal Investigator's Name
: [name]

Research Protocol

1. Study Title

A Randomized phase II clinical trial to evaluate the efficacy of alternating mFOLFOX/mFOLFIRI chemotherapy regimen as a second-line treatment for advanced biliary tract cancer

2. Research Institution information

1) Principal Investigator:

- [name], Division of Hematology/Medical Oncology, Department of Internal Medicine, Seoul National University Bundang Hospital, Seoul National University College of Medicine

Co-Investigators:

- [name], Division of Hematology/Medical Oncology, Department of Internal Medicine, Seoul National University Bundang Hospital, Seoul National University College of Medicine

- [name], Department of Oncology, Gachon University Gil Medical Center

*Additional site-specific investigators will be recruited

2) Research Coordinator:

- [name], Division of Hematology/Medical Oncology, Department of Internal Medicine, Seoul National University Bundang Hospital, Seoul National University College of Medicine

3. Funding and support information

Drug support

- Boryung Pharmaceutical (Oxaliplatin, Irinotecan)

: [name]

Research Funding

- None

4. Expected study duration

※ The study will run for 3 years from the date of IRB approval

: 2 years for enrollment, 1 year for follow-up and data analysis

5. Target disease

- 1) Patients with recurrent or advanced biliary tract cancer who have failed first-line therapy.
 - Biliary tract cancer includes intrahepatic cholangiocarcinoma, extrahepatic cholangiocarcinoma gallbladder cancer, and ampulla of Vater cancer.
 - Patients must have received at least one cycle of gemcitabine/cisplatin-based chemotherapy and shown confirmed disease progression.

6. Background and objectives

1) Background

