- Biliary Tract Cancer (BTC) consists of intrahepatic and extrahepatic cholangiocarcinoma, gallbladder cancer, and ampulla of Vater cancer. BTC is a relatively rare cancer worldwide, with an age-standardized incidence rate (ASIR) of approximately 2.7 cases per 100,000 population, lower than major cancers such as lung, breast, and colorectal cancer. However, the global incidence of BTC has been steadily rising, with higher rates observed in Asia, particularly in Korea, Japan, and China. In the United States, approximately 8,000 BTC cases are reported annually. According to data from the National Cancer Center of Korea, BTC and gallbladder cancer accounted for 2.9% of all cancer cases in Korea in 2020 (7,179 cases, crude incidence rate: 14.0 per 100,000 population), ranking 9th among all cancers. By age group, the highest incidence (35.5%) was observed in individuals in their 70s, indicating that the aging population is expected to contribute to further increases in BTC incidence.
- Surgery remains the primary treatment for BTC; however, only 10% of patients are eligible for surgery at the time of diagnosis, as most are diagnosed at advanced stages. Consequently, systemic chemotherapy is the mainstay of treatment for recurrent or advanced BTC.

In 2010, the ABC-02 trial demonstrated the superiority of gemcitabine plus cisplatin (Gem/Cis) over gemcitabine monotherapy as first-line treatment for BTC (median overall survival: 11.7 vs. 8.1 months; hazard ratio: 0.64, 95% confidence interval [CI]: 0.52–0.80; $p < 0.001$). Gem/Cis has since been established as the standard first-line treatment for BTC. Recently, immune checkpoint inhibitors, such as Durvalumab and Pembrolizumab, in

combination with Gem/Cis have shown significant efficacy, emerging as new standard therapies. However, median overall survival remains modest (Durvalumab + Gem/Cis: 12.8 months; Pembrolizumab + Gem/Cis: 12.7 months), and resistance ultimately leads to disease progression.

- The ABC-06 trial established FOLFOX as the standard second-line therapy for BTC; however, its efficacy is limited, with a median overall survival of 6.2 months, progression-free survival of 4.0 months, and a tumor response rate of only 5%. Furthermore, there is no established standard therapy for third-line treatment. Targeted therapies, such as those targeting FGFR2 fusion, IDH1 mutation, and BRAF mutation, have shown efficacy but are limited in applicability and effectiveness compared to other cancers.

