3) Oxaliplatin

- ✓ Generic Name: Oxaliplatin
- ✓ Trade Name: OXALItin Injection (Manufactured by Boryung Pharmaceutical Co., Ltd.)
- ✓ Formulation: 150mg(5mg/ml) per vial.
- ✓ Indications
 - ① First-line treatment for metastatic colorectal cancer in combination with 5-fluorouracil and folinic acid (leucovorin).
 - ② Adjuvant therapy for Stage III (Duke's C) colorectal cancer after complete resection of the primary tumor in combination with 5-fluorouracil and folinic acid.
 - ③ Unresectable advanced or metastatic gastric cancer.
- ✓ Adverse Effects: Bone marrow suppression, mucositis, and neurological symptoms (paresthesia, dysesthesia).

8. Inclusion Criteria, Exclusion Criteria, Target Sample Size, and Sample Size Justification

- 1) Inclusion criteria (All eligibility criteria must be fulfilled)
 - A. Age \geq 19 years.
 - B. Diagnosed with biliary tract cancer, including intrahepatic cholangiocarcinoma, extrahepatic cholangiocarcinoma, gallbladder cancer, or ampulla of Vater cancer.
 - C. Either unresectable advanced disease or recurrence after curative surgery.
 - D. ECOG (Eastern Cooperative Oncology Group) performance status of 0–2
 - E. First-Line Treatment Failure: Disease progression after at least one cycle of gemcitabine/cisplatin-based therapy or discontinuation of therapy due to adverse effects.
 - F. Presence of evaluable or measurable lesions according to RECIST v1.1 criteria.
 - G. Laboratory Criteria: optimal bone marrow, liver, and kidney function within one week prior to enrollment:
 - A. Hemoglobin $>$ 9.0 g/dL
 - B. Absolute neutrophil count (ANC) $>$ 1,000/uL
 - C. Platelet count $>$ 75,000/uL

- D. Serum creatinine < 1.5× upper limit of normal (ULN)
- E. AST/ALT < 3× ULN
- F. Total bilirubin < 1.5× ULN (*biliary drainage is allowed*).
- H. Patients who understand the study protocol, can provide written informed consent, and are aware of their right to withdraw at any time without penalty.
- I. Effective Contraception (for patients of childbearing potential receiving oxaliplatin):
 - A. Male patients:
Must use effective contraception during the study and for 12 months after treatment completion.
 - B. Female patients:
Must use effective contraception during the study and for 15 months after treatment completion.

< Permitted effective contraceptive methods>

Highly effective contraceptive methods	Effective contraceptive methods

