
 ● Complete Abstinence (Refraining from any sexual activity from the time of consent until the end of the study) ● Oral, vaginal, or transdermal contraceptives containing estrogen and progestin, which suppress ovulation. ● Progestin-only contraceptives, including oral, implantable, or injectable forms, which suppress ovulation. ● Hormone-releasing intrauterine system ● Intrauterine devices (IUDs) with a failure rate of less than 1%. ● Bilateral tubal occlusion or ligation. ● Vasectomy (with documented azoospermia confirmed by semen analysis, conducted at least 90 days after the procedure). 	
 ● Progestin-only oral hormonal contraceptives where ovulation suppression is not the primary mechanism of action. ● Male or female condoms, with or without spermicide. ● Caps, diaphragms, or sponges containing spermicide. ● Combination of a cap, diaphragm, or sponge containing spermicide with a male condom (dual barrier method).
Contraceptive Methods Not Permitted	
	
 ● Periodic Abstinence (e.g., calendar method, symptothermal method, post-ovulation method). ● Withdrawal Method (Coitus Interruptus) ● Spermicide Alone ● Lactational Amenorrhea Method (LAM)

2) Exclusion Criteria (Patients meeting any of the following criteria will be excluded from the study.)

- A. Patients with prior exposure to oxaliplatin or irinotecan in previous cancer treatments.
- B. Patients with metastatic or unresectable biliary tract cancer who have received second-line or higher chemotherapy.
- C. Pregnant or breastfeeding women.
- D. Patients with a history of other malignancies within the past 3 years, except for papillary or follicular thyroid cancer.
- E. Patients with uncontrolled infections or other systemic diseases.
- F. Patients with a history of myocardial infarction, unstable angina, or heart failure (NYHA Class III-IV) within the last 6 months.
- G. Patients with Grade 3 or higher peripheral neuropathy caused by prior chemotherapy.
- H. Patients with known allergic reactions to the investigational drugs.
- I. Known patients with Gilbert's syndrome, DPD (dihydro-pyrimidine dehydrogenase) deficiency, or Homozygous UGT1A1*28 alleles.
- J. Patients currently taking potent CYP3A4 inhibitors (e.g., ketoconazole, itraconazole, ritonavir, clarithromycin), or potent CYP3A4 inducers (e.g., rifampin, carbamazepine, St. John's Wort).

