- L. Patients who are eligible for targeted therapy, including FGFR inhibitors or IDH1 inhibitors. (eligible for patient who unable to use these targeted agents due to drug cost.)
- M. Patients with active CNS metastases and/or carcinomatous meningitis.
- N. Patients who meet contraindications for the investigational drugs as per domestic regulatory guidelines, including patients with infections, Interstitial pneumonitis or pulmonary fibrosis, Severe diarrhea, Chronic inflammatory bowel disease, Intestinal paralysis or obstruction, Functional impairment due to peripheral sensory neuropathy, Severe renal dysfunction.
- K. Patients deemed ineligible by the investigator for any other reason.

3) Target sample size and calculation basis

Assuming a 6-month survival rate of 50% for the mFOLFOX group and 75% for the

mFOLFOX/mFOLFIRI group, a total of 58 evaluable patients per group is required to achieve 80% power at a significance level of $p=0.05$.

Considering a 10% drop-out rate, 65 patients per group need to be randomized, resulting in a total of 130 patients for the study. The enrollment period is planned for 2 years, with 1 year of follow-up.

4) Plan for enrollment of participants

[figure not shown]
The study will recruit patients who are already receiving treatment, without utilizing a separate [Participant Recruitment Advertisement]. The principal investigator and co-investigators will ensure that potential participants are not excluded from this study based solely on race or socioeconomic status. Efforts will be made to include all eligible patients who meet the inclusion criteria, and potential participants will be fully informed about the purpose of the study. Recruitment will aim to ensure that the study population represents the overall population of biliary tract cancer patients treated at the study institution.

9. Methods

1) Specific research methods

A. Clinical trial design

- 2nd-line treatment, Phase II
- Alternating mFOLFOX / FOLFIRI

< Study design >

- Screening will be conducted between Day -14 and Day 0 (the day of randomization). Radiological assessments for tumor evaluation are valid up to 2 weeks prior to the start of the study (Day 1).
- The initiation criteria for each cycle of chemotherapy administration are ANC > 1.0 × 10⁹/L and platelets > 75 × 10⁹/L.
- The window period for chemotherapy administration visits is set at ±3 days.

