- Response evaluations will be conducted every 8 weeks (after every 2 cycles). The window period is set at ±7 days.
- The administered dose may be rounded to one decimal place.
- The treatment will continue until the occurrence of any of the following events.
 - Disease progression
 - Occurrence of unacceptable adverse effects
 - Withdrawal of consent
- The end-of-treatment visit will be conducted on the day treatment is discontinued or within 30 days of the last administration.
- The survival status will be assessed every 8 weeks after the end-of-study visit, with a window period of ±2 weeks (assessment can be conducted via phone).

B. General principles for chemotherapy dose adjustment

- ① Dose reduction or treatment delay is planned for severe hematologic or non-hematologic adverse events occurring during clinical trial treatment. Dose adjustment should be performed based on the severity of the adverse event in the most severely affected organ system. Adverse events will be graded using NCI CTCAE version 5.0.
- ② If the subject experiences multiple adverse events with conflicting recommendations, the most conservative dose adjustment recommendation will be followed.
- ③ It should be noted that doses reduced due to adverse events cannot be re-escalated.
- ④ All adverse events must be resolved to Grade 1 or lower before resuming treatment. Dose adjustments should be based on the severity of the adverse event in the most severely affected organ system. Missed doses during the treatment cycle should not be made up.
- ⑤ If the investigator determines that an adverse event is unlikely to progress to a severe or life-threatening level (e.g., alopecia, taste alterations), treatment will continue at the same dose without dose reduction or interruption. Additionally, (non-hemolytic) anemia can be managed satisfactorily with transfusion, and therefore dose reduction or treatment interruption is not required in such cases.
- ⑥ Dose adjustments for a single abnormal hematologic laboratory value will be based

on hematologic parameters at the start of the treatment cycle. Since specimen collection is not scheduled during the treatment cycle, nadir level measurements will not be conducted.

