- ② Patients who experience clinically severe or persistent side effects that make continued administration difficult (if the next dose is delayed by more than 3 weeks).
- ③ Cases where clinically significant abnormal test results are observed (if the next dose is delayed by more than 3 weeks).
- ④ If the patient wishes to discontinue the treatment.
- ⑤ If the patient refuses to receive the drug administration.
- ⑥ If the patient passes away.
- ⑦ If follow-up observation is not possible.

- ⑧ If the clinical trial investigator deems it necessary for any other reason.

D. End-of-treatment assessment

- ① Vital signs, physical measurements: Height, weight
- ② Clinical laboratory tests
 - a. Hematologic tests: Hemoglobin, hematocrit, WBC (including differential count), platelet count.
 - b. Blood biochemical tests: Total bilirubin, γ -GTP, AST/ALT, alkaline phosphatase (ALP), total protein, albumin, serum creatinine, BUN, tumor markers (CA19-9, CEA), creatinine.
- ③ Radiological measurement of lesions (if needed)
- ④ Clinical findings regarding adverse reactions

E. Follow-up investigation

- ① Adverse events related to the investigational drug and the tumor will be followed up until recovery. The reasons for trial discontinuation and the date of discontinuation must be documented in the case report form for all patients. The investigator is recommended to ensure that all necessary tests and procedures are completed when a participant is excluded from the clinical trial.
- ② The follow-up period begins after the end-of-trial visit and is conducted every 8 weeks. During the follow-up period, the following evaluation variables will be recorded. (Medical record review and survival confirmation can be done by phone):
 - a. Duration until disease progression for patients who did not experience disease progression up to the end of investigational drug administration.
 - b. Third-line treatment (including start date): Additional cancer treatments if known (e.g., chemotherapy, immunotherapy, targeted therapy, radiotherapy, and surgery).
 - c. Confirmation of survival status.

5) Criteria for efficacy evaluation and evaluation methods

- A. Death - Confirm the patient's date of death.

- B. 6-month survival rate - The proportion of patients who are alive at 6 months from the initiation of second-line chemotherapy (analyzed using the survival function).

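### The permitted-methods table ends complete abstinence at the end of the study, which for late enrollees falls short of the 12 or 15 months after treatment required by inclusion criterion I

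*Protocol*

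**What the plan says.** Protocol section 8.1, inclusion criterion I, applies to patients of childbearing potential receiving oxaliplatin. Both regimens in section 9.3 contain oxaliplatin, so it covers both arms.

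- Men: "Must use effective contraception during the study and for 12 months after treatment completion".
- Women: "Must use effective contraception during the study and for 15 months after treatment completion".

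The table of permitted methods follows directly. Its first entry, in the highly effective column, reads "Complete Abstinence (Refraining from any sexual activity from the time of consent until the end of the study" (closing bracket omitted here). It is the only permitted method given both a start and a stop point, and nothing elsewhere in the protocol extends it.

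The timeline is in section 4 ("2 years for enrollment, 1 year for follow-up and data analysis", within 3 years from IRB approval) and in section 8.3 ("The enrollment period is planned for 2 years, with 1 year of follow-up"). Treatment has no fixed length. It continues until progression, unacceptable toxicity or the patient's withdrawal.

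**The concern.** Criterion I counts its post-treatment period from the patient's own treatment completion. The abstinence entry stops at the end of the study, which is a different clock. For a patient treated early in the trial the difference is harmless, because the study ends after the required period does. For a patient treated late, the study can end first.

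A participant, or a site counselling one, who relies on the table could regard abstinence as complete while the protocol's own post-treatment period is still running. If no other permitted method is then taken up, the protection against pregnancy after cytotoxic chemotherapy lapses early. The consent pages are not in the file, so it cannot be seen which period participants are told, and nothing is alleged about them.

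**Working it through.** The protocol gives no figure to reproduce here, so the check is timeline arithmetic.

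**Inputs**
- Study end, taking the phrase to mean the whole trial: 24 + 12 = month 36 from IRB approval (sections 4 and 8.3).
- Required period after treatment completion: 12 months (men), 15 months (women) (section 8.1, criterion I).
- Enrollment month *e*: up to 24.
- Treatment length *T*: not fixed by the protocol. A range of 1 to 6 months is assumed. The middle value of 4 months is taken from the FOLFOX result cited in section 6.1, "with a median overall survival of 6.2 months, progression-free survival of 4.0 months".

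**Latest treatment completion that is fully covered**
- Men: 36 − 12 = month 24.
- Women: 36 − 15 = month 21.

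**Shortfall**, in months; a value at or below zero means no gap
- Men: *e* + *T* + 12 − 36 = *e* + *T* − 24.
- Women: *e* + *T* + 15 − 36 = *e* + *T* − 21.

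| Enrolled at month | *T* (months) | Men | Women |
|---|---|---|---|
| 12 | 6 | none (−6) | none (−3) |
| 18 | 4 | none (−2) | 1 |
| 18 | 6 | 0 | 3 |
| 24 | 1 | 1 | 4 |
| 24 | 4 | 4 | 7 |
| 24 | 6 | 6 | 9 |

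At *T* = 4 there is no gap for men enrolled by month 36 − 12 − 4 = 20, or for women enrolled by month 36 − 15 − 4 = 17. For a month-24 enrollee the gap is *T* (men) or *T* + 3 (women), so any treatment at all produces one.

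**Alive at study end.** The gap matters only for a patient alive at month 36. For a month-24 enrollee that means surviving 12 months. Assuming a constant hazard:
- 6-month survival of 50% (control assumption): 0.50^(12/6) = 0.25.
- 6-month survival of 75% (experimental assumption): 0.75^(12/6) = 0.5625.
- Cited median survival of 6.2 months: 0.5^(12/6.2) = 0.26.

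**The other reading of the phrase.** Section 9.1 A says "The survival status will be assessed every 8 weeks after the end-of-study visit", and section 9.4 E says "The follow-up period begins after the end-of-trial visit and is conducted every 8 weeks". Both place a study-end or trial-end visit before survival follow-up, at the level of the individual patient. Neither visit is defined or dated, so no figure is put on this reading. It would bring the stop point forward, enlarge the gap and could reach early enrollees too.

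**The case against.** The strongest reply is that criterion I sets the duration in mandatory terms and the table only lists which methods count. For every other method the duration comes from criterion I alone. A patient who stops abstaining early and uses nothing else is in breach whatever the table says. The bracketed definition may be there chiefly to separate continuous abstinence from periodic abstinence, which the same table forbids. On that view the entry is incomplete rather than contradictory. This stands as far as it goes: the requirement is not removed. It does not make the stated stop point correct.

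A second reply is that the case is a corner case. The largest gaps are for someone enrolled in the last month, month 36 is a planning figure, and treatment length is assumed. The patient must also be of childbearing potential, choose abstinence, be alive at study end, resume sexual activity and use no other method, in a disease whose incidence peaks in the 70s (section 6.1). This also stands, and it is why the point ranks low. The group is not empty by design, since the minimum age is 19.

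A third is that the end of the study is undefined, so the figures rest on one reading. That is true, but the reading used is the more lenient one.

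**Conclusion.** The concern holds as a minor wording inconsistency in eligibility and safety text. The abstinence entry does not match the period that criterion I requires.

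On the whole-trial reading the mismatch affects only late enrollees. At 4 months of treatment it reaches 4 months (men) and 7 months (women) for the last patient in. The sizes depend on the assumed treatment length and on the planned 36-month timeline; the mismatch itself depends on neither. The survival range of about 25% to 56% rests on a constant hazard, and its upper end on the hypothesised benefit. The number of patients affected cannot be estimated from the protocol but is likely to be very small. Sample size, endpoints and analysis are untouched.

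**What to change.** Redefine the abstinence entry as refraining from any sexual activity from consent, through the study, and until 12 months (men) or 15 months (women) after treatment completion. Give the same period in the participant information. The shortfall is then zero for every patient, under either reading of the end of the study. The cost is a one-line wording amendment with no procedural or statistical consequence.

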Third event	Dose adjustment will not be applied if continuing treatment is considered beneficial for the participant.	If continuing treatment is considered beneficial for the participant, further dose reduction or omission of certain drugs may be implemented. Otherwise, treatment or study participation will be discontinued.	If the continuation of treatment is determined to be beneficial for the participant, further dose reduction or omission of certain drugs may be applied. Otherwise, treatment or study participation will be discontinued.

★ For mFOLFOX and Neutropenia, It is recommended to first reduce the 5-FU bolus dose by 25% or discontinue it before following the above recommendations in cases of neutropenia. Treatment cannot be initiated unless hematologic adverse events are resolved to ANC > 1.5 × 10⁹/L and platelets > 75 × 10⁹/L. However, in subsequent cycles, participants who had their dose reduced in the previous cycle due to persistent cytopenia may begin treatment at the reduced dose level if ANC ≥ 1.0 × 10⁹/L. For febrile neutropenia, additional dose reductions are permitted at the investigator's discretion, taking into account the patient's safety.

< Dose adjustment for non-hematologic adverse events >

	Grade 2	Grade 3	Grade 4
First event	Wait until recovery to	Wait until recovery to	If the investigator

	grade 0-1, then restart with the full dose from the previous cycle.	grade 0-1, then reduce the dose of Oxaliplatin, Irinotecan, and 5-FU by one level.	determines that discontinuation of the protocol or continuation of treatment is necessary for a specific subject, wait until recovery to grade 0-1, then administer a reduced dose of Oxaliplatin, Irinotecan, and 5-FU by two levels.
The second event of the same non-hematologic adverse reaction	Wait until recovery to grade 0-1, then reduce the dose of Oxaliplatin, Irinotecan, and 5-FU by one level.	Wait until recovery to grade 0-1, then reduce the dose of Oxaliplatin, Irinotecan, and 5-FU by two levels.	Not applicable.
The third event of the same non-hematologic adverse reaction	Wait until recovery to grade 0-1, then reduce the dose of Oxaliplatin, Irinotecan, and 5-FU by two level.	Treatment discontinuation /Study termination	Not applicable.
The fourth event of the same non-hematologic adverse reaction	Treatment discontinuation /Study termination	Not applicable.	Not applicable.

<Expected Adverse Reactions and Management Strategies>

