In cases where neurological toxicity, reversible posterior leukoencephalopathy syndrome, septic shock, disseminated intravascular coagulation, hemolytic uremic syndrome, QT interval prolongation, or rhabdomyolysis are suspected or occur, appropriate treatment should be

administered, and the patient should be referred to a relevant specialist. Based on the investigator's judgment, treatment may be resumed with dose adjustment according to the toxicity grade once recovery is achieved.

2) Control group setting and randomization method

The investigational product will be administered only to participants enrolled in this clinical trial in accordance with the procedures specified in the clinical trial protocol. Participants who withdraw from the trial will retain their participant number. A new participant number must always be assigned to new participants. All eligible participants must be registered prior to the initiation of treatment.

3) Administration/Dosage of investigational products, method of administration, combination therapy, and use of control drugs

The chemotherapy regimens to be used in this clinical trial are mFOLFOX and mFOLFIRI.

The methods of administration and schedules for the drugs are as follows:

A. mFOLFOX (Administered as a single regimen every 2weeks)

1) mFOLFOX
D1
Oxaliplatin 85mg/m ² over 2hr
Leucovorin 400mg/m ² over 2hr
Fluorouracil 400mg/m ²
FU 2400mg/m ² over 46hr

B. mFOLFOX/mFOLFIRI (Administered alternately every 2 weeks.)

1) mFOLFOX	2) mFOLFIRI
D1	D1
Oxaliplatin 85mg/m ² over 2hr	Irinotecan 150mg/m ² over 2hr
Leucovorin 400mg/m ² over 2hr	Leucovorin 100mg/m ² over 2hr
Fluorouracil 400mg/m ²	5FU 2400mg/m ² over 46hr

FU 2400mg/m ² over 46hr	
------------------------------------	--

- The treatment will continue to be repeated until disease progression occurs, treatment is no longer feasible due to toxicity, or the patient declines further therapy.

4) Observation parameters, clinical laboratory tests, and methods of assessment

<Clinical study tests and observation items, schedule >

- A. The screening procedures must be conducted within 14 days prior to the initiation of treatment. (Screening tests may be used as Day 1 Cycle 1 tests.) Evaluation timeline: Day -14 to Day -1 (before drug administration)
 - ① Informed Consent: A signed consent form in the designated format.
 - ② Vital Signs and Physical Measurements: Body temperature, blood pressure, heart rate, height, and weight.
 - ③ ECOG Performance Status

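### Section 9.1 A starts each cycle at ANC > 1.0 × 10⁹/L and the note in 9.1 C requires > 1.5 after a hematologic event, but the protocol does not say how the two rules fit together

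*Protocol*

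**What the plan says.** All ANC values here are × 10⁹/L.

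- **Section 9.1 A, Clinical trial design:** "The initiation criteria for each cycle of chemotherapy administration are ANC > 1.0", together with platelets > 75. The sentence names no regimen, makes no exception and does not refer to 9.1 C.
- **Section 9.1 C, starred note under the hematologic table:** "Treatment cannot be initiated unless hematologic adverse events are resolved to ANC > 1.5", again with platelets > 75. One relaxation follows for later cycles. It covers only "participants who had their dose reduced in the previous cycle due to persistent cytopenia". The lower limit set for this group reads: "may begin treatment at the reduced dose level if ANC ≥ 1.0".
- **Same note, opening words:** "For mFOLFOX and Neutropenia, It is recommended to first reduce the 5-FU bolus dose by 25% or discontinue it". The note does not mention mFOLFIRI.
- **Section 9.1 C, hematologic table:** ANC from 1.0 to below 1.5 has its own column. Its entry for the first and second event is that the dose stays unchanged.
- **Section 9.3, regimens:** the control arm is "mFOLFOX (Administered as a single regimen every 2weeks" and the experimental arm is "mFOLFOX/mFOLFIRI (Administered alternately every 2 weeks".

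**The concern.** Both sentences decide whether a patient may be treated on a given day, and they use different ANC limits. A site working from the start criteria in the design section would treat a recovering patient at ANC 1.2. A site working from the note would not. Each could cite the protocol.

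This is a dosing-day safety rule in a trial that section 2 plans at more than one institution. Holding a patient can lengthen a delay, and a delay of more than 3 weeks is a discontinuation condition in sections 9.4 C and 9.8, although 9.1 B item 7 allows treatment to continue in some cases. Whether such a patient is dosed or held should not depend on which page the site consults.

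**Working it through.** There is no stated figure to reproduce, so the check applies each rule to the same patient.

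**Inputs.** 9.1 A permits a start if ANC > 1.0. The note permits a start after a hematologic adverse event if ANC > 1.5, or if ANC ≥ 1.0 when the previous cycle was reduced for persistent cytopenia. The platelet limit is > 75 in 9.1 A and in the note's main rule, so platelets are taken as above 75 and only ANC differs.

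**Result after a hematologic adverse event.** Each cell shows whether 9.1 A / the note permits a start.

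| Previous cycle | ANC 0.9 | 1.0 | 1.2 | 1.5 | 1.6 |
|---|---|---|---|---|---|
| Full dose | no / no | no / no | **yes / no** | **yes / no** | yes / yes |
| Reduced for a non-hematologic event | no / no | no / no | **yes / no** | **yes / no** | yes / yes |
| Reduced for persistent cytopenia | no / no | **no / yes** | yes / yes | yes / yes | yes / yes |

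The main disagreement is 1.0 < ANC ≤ 1.5, a band of 1.5 − 1.0 = 0.5, for patients outside the exception. Two examples:

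- The previous cycle was at full dose, ANC is 0.8 on the scheduled day and 1.2 on retest. Any reduction for this event begins with the coming cycle, so the exception is not met.
- The same ANC values occur in a patient whose previous cycle was reduced under the non-hematologic table ("Wait until recovery to grade 0-1, then reduce the dose of Oxaliplatin, Irinotecan, and 5-FU by one level"). That reduction was not for cytopenia, so the exception is again not met.

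A minor mismatch exists inside the exception at exactly 1.0, where 9.1 A uses > and the note uses ≥.

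**Does the hematologic table settle it?** No. It does not say whether an ANC of 1.0 to below 1.5 alone counts as an event that triggers the > 1.5 condition. If it does, a patient whose only finding is ANC 1.2 on the scheduled day may start under 9.1 A, keeps the same dose under the table, and may not start under the note. Because the first and second such events lead to no reduction, they would not bring the patient into the exception either.

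**Does another clause rank the two thresholds?**

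- 9.1 B item 2 prefers the most cautious dose adjustment when several adverse events point different ways. It does not address two start limits for one ANC value.
- 9.1 B item 4 requires recovery to Grade 1 or lower. It gives no ANC value and mentions neither rule.
- 9.1 C leaves dose reductions to institutional guidelines and investigator judgement, and lets the hematologic criteria follow domestic approval conditions. Both clauses add flexibility, but neither says which limit governs.

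**Scope of the note.** The opening label introduces advice on the 5-FU bolus. In section 9.3 the mFOLFOX column lists a 400 mg/m² fluorouracil dose and the mFOLFIRI column does not, so the label most naturally limits only that advice. The > 1.5 sentence speaks of hematologic events in general and includes platelets, which is wider than neutropenia. Its application to mFOLFIRI cycles is therefore likely but not stated.

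**The case against.** The best defence is that the two texts work in sequence. 9.1 A is the general floor, the note adds a stricter condition for the first recovery from a hematologic event, and its exception then returns to about 1.0 for patients already reduced. Holding a patient at 1.2 satisfies both texts. 9.1 C is also openly adjustable, so some variation between sites was accepted. The permissive limit matches the eligibility criterion of ANC above 1,000/uL.

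Much of this stands. The sequence is plausible, and the exception confines the problem: doses are not re-escalated (9.1 B item 3), so for a patient reduced for persistent cytopenia the > 1.5 condition matters mainly at the first recovery. The defence fails on one point. The sequence has to be inferred, while 9.1 A says in plain terms that its criterion holds for each cycle. A site that applies it literally doses a patient whom the note bars.

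A reader might go further and infer that the arms are held to different rules, since every control administration is mFOLFOX and the experimental arm alternates. The document does not support that. The inference needs the label to limit the whole note, which is the weaker reading. Even then the > 1.5 condition applies only after a hematologic event outside the exception, so the share of mFOLFOX administrations in each arm does not measure how often the rule is used.

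**Conclusion.** The inconsistency is real and limited. After a hematologic adverse event, outside the stated exception, 9.1 A and the note give opposite answers for 1.0 < ANC ≤ 1.5, and no clause says which governs. Two smaller gaps accompany it: the table does not say whether its 1.0 to below 1.5 column alone triggers the note, and the note does not say whether its start condition covers mFOLFIRI cycles.

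This rests on the text alone. The number of patients affected is not derivable from the protocol, and neither an imbalance between arms nor an effect on 6-month survival is shown. The point should be corrected because it concerns a safety rule and is cheap to settle. The statistical design does not depend on it.

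**What to change.** Reconcile 9.1 A, the hematologic table and the starred note in 9.1 C. Sections 9.1 A and 9.1 C should refer to each other and state consistently:

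- when each ANC start threshold applies, including for a patient whose previous cycle was reduced for a non-hematologic reason;
- whether ANC of 1.0 to below 1.5 alone counts as an event for the note;
- how the note relates to the grade-based recovery rule in 9.1 B item 4;
- whether the note's start condition covers mFOLFIRI cycles;
- the same inequality at 1.0 in both places.

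One rule or two tiers would both be workable if stated. The choice and the values belong to the clinical team, and none is proposed here. The cost is one clarifying amendment and a notice to sites, with no change to sample size or visits.
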